10.3 Prior and Concomitant Medications and Other Study Restrictions

All medications (including herbal medicines and supplements) administered from 60 days before the Screening Visit through the Safety Follow-up Visit will be recorded in the source documents and on the electronic case report form (eCRF).

Subjects will be questioned at each study visit regarding use of medications during the period since the last visit. All medications used during the period will be recorded in the eCRF.

NSAIDs: Subjects may continue treatment with one NSAID (additional aspirin [second NSAID] ≤325 mg/day is allowed) at a dose that is stable for at least 28 days before Day 1, which must remain the same throughout the study. Any increase, decrease, or change in the dose of the one NSAID (not including aspirin) is prohibited during a subject's participation in the study, except for a dose reduction that is mandated for NSAID toxicity. NSAIDs are not stopped for the analgesic holiday before joint count assessments.

Systemic Corticosteroids: Subjects may continue treatment with prednisone ≤10 mg/day (or equivalent; Section 16.13), which must be a stable dose for at least 28 days before Day 1. Any increase, decrease, or change in the dose of systemic corticosteroid is prohibited during a subject's participation in the study, except for a dose reduction that is mandated for corticosteroid toxicity. Intraarticular corticosteroids are prohibited in any joint within 4 weeks before screening, and within 12 weeks before screening for the MRI-designated hand or joint planned for arthroscopy. Intraarticular corticosteroid injections are prohibited throughout the study (see Section 10.2), although this option may be discussed with the medical monitor if required to prevent early discontinuation (Section 9.1.4).

Live, Attenuated Vaccinations: Subjects who receive study drug should not receive any type of live or attenuated live vaccinations in the 4 weeks before study Day 1, during the study, or within 4 weeks after the final dose of study drug.

Drug-Drug Interactions: Any moderate or strong CYP3A or P-gp inhibitors or inducers as well as CYP3A sensitive substrates will be prohibited during the study; a partial list of prohibited medications is provided in Section 16.3.

Preliminary analysis of the PK data from a drug-drug interaction study of VX-509 and midazolam shows a strong inhibition of the CYP3A isozyme by VX-509 and its metabolite, M3. A mean 13-fold increase in overall midazolam exposure (AUC_{last}) and 3-fold mean increase in peak midazolam exposure (C_{max}) were observed when VX-509 was coadministered with midazolam, a drug which is extensively metabolized by CYP3A (CYP3A substrate). Therefore, a subject's exposure to medications that are metabolized extensively via CYP3A may increase significantly when coadministered with VX-509. As a result of this finding:

- Avoid concomitant use of VX-509 with sensitive CYP3A medications with serious side effects at high exposure (i.e. narrow therapeutic window, prolonged QTc).
- Use caution with administration of other CYP3A-metabolized medications, and/or consider use of alternative medications if appropriate.
- Discuss any questions regarding concomitant medications, and/or study eligibility, with the Study Medical Monitor.
- Remind patients to inform the investigator of all medications they are taking, including prescription and non-prescription medications or herbal remedies.

Non-narcotic Analgesic Medications (other than NSAIDs): Subjects are permitted to use acetaminophen/paracetamol as a supplemental analgesic medication during the study. The dose should not exceed 4 g/day. These medications must not be taken during the full 24 hour day before, and on the day of each joint assessment until the joint counts are completed, including the assessment on Day 1 dosing.

Narcotic Analgesic Medications: Subjects are permitted to take tramadol, codeine, oxycodone, or codeine/oxycodone based combination analgesics on an as needed (prn) basis if prescribed by a physician for their RA. Subjects are not permitted to use other opiates. These medications must not be taken during the full 24 hour day before, and on the day of each joint assessment until the joint counts are completed, including the assessment on Day 1 before dosing.

DMARDs: For study eligibility (Section 10.1), subjects must be receiving stable therapy with 1 of the following DMARDs: methotrexate, sulfasalazine, leflunomide, anti-malarial drug, or penicillamine. Stable therapy with 1 anti-malarial drug may be continued alone or with 1 of the other DMARDs. Stable therapy is defined as initiation of the DMARD/anti-malarial drug at least 16 weeks before screening and no change for the 8 weeks immediately before screening. The DMARD/anti-malarial dose must remain the same throughout the study. Any increase, decrease, or change in the DMARD/anti-malarial dose is prohibited

during a subject's participation in the study, except for a dose reduction that is mandated for toxicity. The required dose ranges for each of these DMARDS are provided below:

Methotrexate and Folate/Folinic acid: If a concomitant medication at screening, methotrexate at doses of 15 to 25 mg per week (oral, intramuscular) may be continued at a stable dose throughout the trial, coadministered with folic or folinic acid \geq 5 mg/week. For subjects with documented toxicity at a methotrexate dose of 15 mg/week, a stable methotrexate dose of \geq 7.5 mg/week is acceptable. Subjects who discontinued methotrexate before study entry must have at least a 45-day washout period before screening (Section 16.2).

Sulfasalazine: If a concomitant medication at screening, sulfasalazine at doses of 1 to 2 g/day may be continued at a stable dose throughout the study. Subjects who discontinued sulfasalazine before study entry must have at least a 45-day washout period before screening (Section 16.2).

Leflunomide: If a concomitant medication at screening, leflunomide at doses of 10 to 20 mg/day may be continued at a stable dose throughout the study. Subjects who discontinued leflunomide before study entry must have received cholestyramine and have at least a 28-day washout period before screening (Section 16.2).

Penicillamine: If a concomitant medication at screening, penicillamine at doses of 250 to 750 mg/day may be continued at a stable dose throughout the study. Subjects who discontinued penicillamine before study entry must have at least a 60-day washout period before screening (Section 16.2).

Anti-Malarials: If a concomitant medication at screening, hydroxychloroquine at doses of ≤200 mg bid (or equivalent dose chloroquine) may be continued at a stable dose throughout the study. Subjects who discontinued an anti-malarial drug before study entry must have at least a 28-day washout period before screening (Section 16.2).

Prohibited Non-Biologic DMARD Medications: All other non-biologic DMARDs (gold, azathioprine, mycophenolyate, others) are prohibited from screening until the Safety Follow-up Visit or early discontinuation. Refer to Section 16.2 for the non-biologic DMARD washout periods before screening which are required for study eligibility.

Prohibited Biologic DMARD Medications Including TNF Inhibitors: All biologic DMARDs are prohibited from screening until the Safety Follow-up Visit or early discontinuation. Refer to Section 16.2 for the biologic DMARD washout periods before screening which are required for study eligibility.

Any other medication that might interfere with study evaluations is prohibited. In case of uncertainty, the investigator or designee should contact the Vertex/CRO medical monitor. Subjects are not permitted to participate in investigations of other medications during this study.

10.4 Removal of Subjects in the Study

See Section 9.1.4 for specific rules about consideration for discontinuation related to safety monitoring.

In addition, subjects may withdraw at any time at their own request, and subjects may be withdrawn at any time at the discretion of the investigator or Vertex for safety, behavioral, or administrative reasons. If a subject does not return for a scheduled visit, every effort should be made to contact the subject. In any circumstance, every effort should be made to document subject outcome, if possible. The investigator should inquire about the reason for withdrawal, request that the subject return all unused investigational product(s), request that the subject return for a final Safety Follow-up Visit, if applicable, and follow-up with the subject regarding any unresolved adverse events.

Subjects who prematurely discontinue treatment in this study for any reason will complete the Week 12/Early Treatment Termination assessments. Subjects who withdraw will be asked to return to the site, if they consent, for the Safety Follow-up Visit at 28 (± 7) days after their last dose of study drug. The assessments to be conducted during the Safety Follow-up Visit are listed in Table 3-2.

10.5 Replacement of Subjects

Subjects who withdraw or are withdrawn during the study will not be replaced.

11 STUDY DRUG ADMINISTRATION AND MANAGEMENT

11.1 Preparation and Dispensing

Study drug may be dispensed only under the supervision of the investigator or an authorized designee and only for administration to the study subjects.

11.2 Administration

VX-509 tablets or VX-509-matching placebo tablets will be administered orally for each treatment arm described in Section 9.1. VX-509-matching placebo tablets contain the same excipients as VX-509 tablets (microcrystalline cellulose, lactose monohydrate, croscarmellose sodium, colloidal silicon dioxide, sodium lauryl sulfate, magnesium stearate).³⁶

Subjects will be dispensed drug on Day 1 and will be provided additional drug at subsequent visits as needed.

The investigator or designee should explain the correct use of the study drug to each subject. Subjects should be instructed how to replace any lost or missed doses of VX-509 (or placebo).

Subjects should be instructed to always consult with the investigator before replacing any lost or missed doses of VX-509 or placebo.

In order to maintain the blind in the study, each subject in each cohort will receive the same number of tablets at each dosing occasion. Six tablets will be administered at each dosing occasion for each treatment arm for 12 weeks:

Arm A	Placebo	6 × VX-509-matched placebo tablets
Arm B	100 mg VX-509 qd	$2\times50\text{-mg}$ tablets and $4\times VX\text{-}509\text{-matched}$ placebo tablets
Arm C	200 mg VX-509 qd	$4\times50\text{-mg}$ tablets and $2\times VX\text{-}509\text{-matched}$ placebo tablets
Arm D	300 mg VX-509 qd	6×50 -mg tablets

VX-509 should be administered at approximately the same time every day, throughout the study. No restriction is placed for ingestion of food, except on Day 1 when the PK samples are taken after dose.

On Day 1, the first VX-509 dose should be administered at the study site, after the predose PK blood sample is taken. Subjects will be instructed to stay at the study site for a minimum of 4 to 6 hours after administration of the morning dose of study drug until all required clinical assessments are obtained (Section 12.4.1). Subjects should be restricted from food and drink intake (except water) at least 8 hours before dosing and until 2 hours after dosing.

11.3 Dose Modification for Toxicity

Modifications of the study drug dose are prohibited. The exception will be the synovial biopsy subjects, who will be allowed to make dose reductions after discussion with the Vertex medical monitor.

If study drug dosing must be interrupted due to an adverse event or laboratory abnormality, the subject may be restarted or terminated from the study after discussion with the Vertex medical monitor. Specific instructions for interruption for elevated liver function tests are provided in Section 12.9.3.

11.4 Method of Assigning Subjects to Treatment Groups

Each subject will be assigned a unique screening number by the study site before evaluation of inclusion and exclusion criteria at screening. Subjects who satisfy inclusion and exclusion criteria will receive a unique subject number on Day 1, before the first dose, according to a predetermined randomization schedule.

Personnel at the study site will contact the interactive voice/web response system (IVRS/IWRS) for subject enrollment and randomized treatment assignment. The IVRS/IWRS will assign subjects at a ratio of 1:1:1:1 to 1 of the 4 treatment groups, with stratification based on previous use of any biologic response modifier drug (including anti-TNF) for RA. The subjects who additionally undergo synovial biopsy will be an exception and will only be randomized to Arm C.

The randomly assigned subject number in the IVRS/IWRS will be used to identify the individual subject for the duration of the study. Appropriate study drug will be dispensed for each subject based on the randomization information from IVRS/IWRS.

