9 STUDY DESIGN

9.1 Overview of Study Design

This is a Phase 2, randomized, placebo-controlled, double-blind, dose-ranging, multicenter study of VX-509 in subjects with moderate to severe RA who are seropositive or have demonstrated erosive disease, and an inadequate response to a DMARD.

Subjects who have been on a stable dose of DMARD (Section 10.3) must have a swollen joint count of ≥ 6 out of 66 assessed joints and a tender joint count of ≥ 8 out of 68 assessed joints, and a CRP level $\geq 1.2 \times$ the upper limit of normal (ULN) or Westergren erythrocyte sedimentation rate $\geq 1.2 \times$ ULN to qualify for the trial. MRI of the most swollen hand (2+ synovitis of wrist or ≥ 2 MCPs) at baseline will be performed before dosing and at Weeks 6 and 12. A subset of approximately 6 (no more than 10) subjects will undergo arthroscopic synovial biopsies before the first dose at baseline (Day 1) and at Week 4 (Synovial Biopsy Subset).

Subjects will be randomized with stratification based on prior use of biological response modifiers (including a tumor necrosis factor [TNF] inhibitor). VX-509 will be coadministered with DMARD for a planned duration of 12 weeks. Approximately 40 subjects will be randomized to 1 of 4 dosing regimens at a 1:1:1:1 ratio. VX-509-matched placebo tablets will be used to maintain the double-blind. As an exception, the subjects in the Synovial Biopsy Subset will only be randomized to the 200 mg qd dose of VX-509 (Arm C). Subjects in the Synovial biopsy Subset will know that they are not receiving placebo, but not the dose they are receiving.

Arm A. Placebo (N = 10)
Arm B. 100 mg VX-509 qd (N = 10)
Arm C. 200 mg VX-509 qd (N = 10)
Arm D. 300 mg VX-509 qd (N = 10)

The protocol has optional interim analyses (IA) for the purpose of selecting appropriate dose(s) for a subsequent pivotal trial (Section 13.3.4.7). No changes in study design or conduct will be made based on the results of an IA.

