9.2 Rationale for Study Design and Study Drug Regimens

9.2.1 Study Design

The study is designed to evaluate early response to VX-509 administration, including local synovial and bone response assessment by MRI imaging and synovial biopsy (Section 6.5). The double-blind placebo-controlled design will allow comparison to variability in efficacy parameters for control subjects. No blinded joint assessor is utilized in the trial due to the small subject numbers and partial unblinding of all arthroscopy subjects, who are randomized to the 200 mg qd dose of VX-509 (Arm C) to avoid the variability inherent with doseranging. Due to the increased assay sensitivity of joint MRI, and blinded reading by 2 central readers, there is improved study power to detect RAMRIS differences and the validity of MRI data is maintained. As a sensitivity analysis, the ACR20-CRP and DAS28-4(CRP) efficacy parameters will be re-evaluated without inclusion of the arthroscopy subjects.

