13 STATISTICAL AND ANALYTICAL PLANS

Analysis of all data, including safety, PK profiles, efficacy, and synovial biopsies will be performed by Vertex or designee. The results of all parts of the study will be reported in the clinical study report. A detailed analysis plan for the analysis of safety data and efficacy data will be presented in a statistical analysis plan (SAP), and a detailed analysis plan for PK profiles will be presented in a clinical pharmacology analysis plan (CPAP) before the database is locked for analysis.

As synovial biopsy subjects will only be randomized to the 200 mg qd VX-509 dose (Arm C), potential bias is introduced related to patient selection, subjective assessments, and other subject interactions. To minimize the impact of this potential bias, subjects in the Synovial Biopsy Subset will know that they are not receiving placebo, but not the VX-509 dose they are receiving. Centrally blinded MRI reading limits the potential impact on RAMRIS scores.

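### Biopsy subjects are directly assigned to 200 mg yet pooled in the primary between-arm comparisons, and the protocol does not say whether they count toward Arm C's 10

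*Protocol*

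**What the plan says.** Section 9.1 sets the allocation: "Approximately 40 subjects will be randomized to 1 of 4 dosing regimens at a 1:1:1:1 ratio", with N = 10 listed for each of Arms A to D. Section 11.4 repeats it for the assignment system: "The IVRS/IWRS will assign subjects at a ratio of 1:1:1:1 to 1 of the 4 treatment groups", stratified by prior use of a biologic response modifier. Both sections then make an exception. Section 9.1 gives its size: "A subset of approximately 6 (no more than 10) subjects will undergo arthroscopic synovial biopsies". Section 11.4 gives the rule: "The subjects who additionally undergo synovial biopsy will be an exception and will only be randomized to Arm C". Neither section says whether these subjects count toward Arm C's 10, or what ratio then applies to everyone else.

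The subset differs from the other subjects in several ways:

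- It is recruited at selected sites and needs separate consent for the surgical procedure (section 12.5).
- It must have 2+ synovitis of a knee or of the wrist not imaged by MRI (section 10.1, criterion 9).
- It is told that it is not on placebo, though not the dose (sections 9.1 and 11.10).
- It alone is exempt from the bar on dose modification (section 11.3).

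Section 9.2.1 adds: "No blinded joint assessor is utilized in the trial due to the small subject numbers", and gives the partial unblinding of the arthroscopy subjects as a further reason.

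Section 13.2 defines the Full Analysis Set as every randomised and dosed subject, and the MRI Set is drawn from it, so the biopsy subjects are in the primary analyses. Section 13 concedes that "potential bias is introduced related to patient selection, subjective assessments, and other subject interactions". Sections 9.2.1 and 13.3.3.4 plan re-analyses of ACR20-CRP and DAS28-4(CRP) without these subjects.

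**The concern.** A comparison of randomised arms attributes a difference to dose because chance decided who received which dose. For the biopsy subjects chance decided nothing. The 200 mg estimate therefore mixes the drug effect with differences in site, disease pattern and willingness to undergo arthroscopy. For outcomes that rest on joint counts and self-report, it also carries expectation. The ACR20-CRP and DAS28-4(CRP) trend tests run through the same arm. Keeping the dose from these subjects does nothing about selection, or about their knowing they are on active drug.

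The results are meant to inform the Phase 3 dose (sections 6.5, 13.1 and 13.3.4.7), so what matters is the ordering and spacing of the dose estimates rather than significance. The silence on Arm C's quota adds to the problem. It decides whether the planned exclusion analysis has a usable 200 mg arm, and no later analysis plan can supply randomised subjects who were never assigned.

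**Working it through.** **Inputs.** Total about 40, 1:1:1:1, N = 10 per arm, biopsy subset b = 6 (maximum 10), all from section 9.1. ACR20-CRP rates of 25%, 38%, 60% and 65%, and power of about 25% for 300 mg against placebo, from section 13.1. No alpha or test is named there; I assume two-sided 0.05.

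**Step 1: the plan's own figure.** With 10 against 10 and 65% against 25%, exact enumeration of Fisher's test gives 24.5%, and the continuity-corrected normal approximation gives 25.2%. The uncorrected normal formula gives 43.0% and does not match. The stated 25% therefore reproduces, and it rests on 10 per arm.

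**Step 2: arm sizes (A/B/C/D).** If biopsy subjects are outside the list, each arm receives (40 − b)/4 randomised subjects and Arm C receives b more. If they fill Arm C, it has 10 − b randomly assigned subjects.

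| Reading | b = 6 | b = 10 | Biopsy share of Arm C |
|---|---|---|---|
| Within 40, others 1:1:1:1 | 8.5/8.5/14.5/8.5 | 7.5/7.5/17.5/7.5 | 6/14.5 = 41%; 10/17.5 = 57% |
| Within 40, 10 per arm | non-biopsy 10/10/4/10 | non-biopsy 10/10/0/10 | 60%; 100% |
| On top of 40 | 10/10/16/10 (46) | 10/10/20/10 (50) | 6/16 = 38%; 10/20 = 50% |

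No row gives both 10 per arm and 1:1:1:1 among the non-biopsy subjects.

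**Step 3: what the exclusion analysis then has at 200 mg.** Under the first row it has 8.5 (or 7.5) subjects, a balanced randomised comparison. Under the second it has 4 or none. At 4 against 10, Fisher power for 60% against 25% is about 15%, compared with 18% at 10 against 10. Both are low; the larger loss is that 4 subjects give almost no estimate, and 0 give none.

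**Step 4: size of an expectation effect (assumption).** Let knowledge of active treatment raise ACR20 among biopsy subjects by d points. The shift in Arm C's rate is d × b / n(C).

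- b = 6 of 10: 10 × 0.6 = 6 and 20 × 0.6 = 12 points.
- b = 6 of 14.5: 10 × 6/14.5 = 4 and 20 × 6/14.5 = 8 points.

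**Step 5: effect on the ordering of doses.** Take true rates of 60% (200 mg) and 65% (300 mg) and count, by exact binomial convolution, how often the observed 200 mg rate exceeds the 300 mg rate.

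| Arm C against Arm D | d = 0 | d = 10 | d = 20 |
|---|---|---|---|
| 4 + 6 biopsy against 10 | 32% | 43% | 54% |
| 0 + 10 biopsy against 10 | 32% | 50% | 70% |
| 8 + 6 biopsy against 8 | 40% | 48% | 56% |

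**The case against.** Four points on the other side deserve weight.

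1. A reader might infer that 1:1:1:1 and 10 per arm flatly contradict each other. They do not. As arm totals, 10:10:10:10 is 1:1:1:1 if biopsy subjects fill Arm C; the cap of 10 fits that reading, the group is labelled an exception, and the total is only approximate. The incompatibility is confined to 10 per arm together with 1:1:1:1 among the non-biopsy subjects.

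2. A reader might also infer that biopsy subjects make up 60 to 100% of Arm C and that the exclusion analysis cannot work. Both hold only if they fill the quota. If they are assigned outside the list, they are 41 to 57% of the arm, and the planned exclusion analysis is already the randomised comparison for two of the five primary endpoints.

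3. The bias is disclosed, the single dose is justified in section 9.2.1 as avoiding dose-ranging variability, and a sensitivity analysis is pre-specified. This stands. It shows awareness, but the pooled estimate remains primary.

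4. Section 13.1 names RAMRIS as the dose-ranging information for Phase 3, and two central readers score it blinded to dose and chronology. That limits reader bias, so the ACR20 illustration should not be carried over to RAMRIS. It does not remove selection bias, and no exclusion analysis is planned for RAMRIS. Section 13.3.4.7 also allows clinical efficacy data into a dose-selection interim analysis.

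The 10 to 20 points have no source in the protocol, and even without bias the ordering of 200 and 300 mg is often reversed at these sizes.

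**Conclusion.** The point holds. About 6, at most 10, subjects reach 200 mg without randomisation, differ at entry and in what they know, and are pooled in the primary comparisons as if randomised. The stated safeguard is secondary, omits the synovitis, osteitis and erosion endpoints, and may have only 4 or 0 subjects at 200 mg because the quota is undefined.

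The direct assignment, the pooling and the undefined quota are read from the text, and the arm sizes follow by arithmetic. The size of the bias is not known: the 6 to 12 point shift (6 of 10) or 4 to 8 point shift (6 of 14.5) rests on an assumed effect on ACR20. A reader might go further and conclude that the Phase 3 dose choice would be wrong. The documents do not support that. They show that the 200 mg estimate is confounded in a way that can be avoided.

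**What to change.** 1. **Sections 9.1 and 11.4.** State that biopsy subjects are directly assigned to Arm C outside the 1:1:1:1 list and do not count toward its randomised quota, and that all other subjects are randomised 1:1:1:1. Restate the arm sizes, and restate the power in section 13.1, which rests on 10 per arm.

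2. **Sections 13.2 and 13.3.3.** Make the subjects randomised 1:1:1:1 the primary population for every between-arm comparison and trend test, including the RAMRIS endpoints. Keep the pooled Full Analysis Set analysis as supportive, and report the biopsy subjects separately.

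**Cost.** This needs a change to the assignment-system specification and to the analysis text, and no extra subjects. For ACR20-CRP and DAS28-4(CRP) it promotes an analysis already planned. If the total stays at 40, each arm has 10 − 8.5 = 1.5 fewer randomised subjects with 6 biopsy subjects, or 10 − 7.5 = 2.5 fewer with 10. Fisher power for 65% against 25% is about 24% at 8 per arm and 16% at 7, against 24.5% at 10. It does not fall smoothly because the test is discrete. In a study that declares itself not powered against placebo, that is a modest price for an unconfounded 200 mg estimate.
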